6.4.4. Placebo Multiple Imputation

The Placebo Multiple Imputation (pMI) methodology will be used as a sensitivity analysis for the analysis of the primary efficacy endpoint (IGA 0 or 1 at Week 16) as well as the key secondary endpoints at Week 16. In these sensitivity analyses the primary censoring rule will be applied.

The pMI assumes that the statistical behavior of drug- and placebo- treated patients after the occurrence of intercurrent events will be the same as if patients were treated with placebo. Thus, in the effectiveness context, pMI assumes no pharmacological benefit of the drug after the occurrence of intercurrent events but is a more conservative approach than mLOCF because it accounts for uncertainty of imputation, and therefore does not underestimate standard errors, and it limits bias. In the efficacy context pMI is a specific form of a missing not at random analysis and expected to yield a conservative estimate of efficacy.

In the pMI analysis, multiple imputations are used to replace missing outcomes for drug- and placebo-treated patients who have an intercurrent event using multiple draws from the posterior predictive distribution estimated from the placebo arm. The binary outcomes will then be derived from the imputed data.

Data are processed sequentially by repeatedly calling SAS® PROC MI to impute missing outcomes at visits $t=1, \dots, T$.

1. *Initialization:* Set $t=0$ (baseline visit)
2. *Iteration:* Set $t=t+1$. Create a data set combining records from drug- and placebo-treated patients with columns for covariates \mathbf{X} and outcomes at visits $1, \dots, t$ with outcomes for all drug-treated patients set to missing at visit t and set to observed or imputed values at visits $1, \dots, t-1$.
3. *Imputation:* Run Bayesian regression in SAS® PROC MI on this data to impute missing values for visit t using previous outcomes for visits 1 to $t-1$ and baseline covariates. Note that only placebo data will be used to estimate the imputation model since no outcome is available for drug-treated patients at visit t .
4. Replace imputed data for all drug-treated patients at visit t with their observed values, whenever available up to permanent study drug discontinuation and/or rescue (if censoring on rescue). If $t < T$ then go to Step 2, otherwise proceed to Step 5.
5. Repeat steps 1-4, m times with different seed values to create m imputed complete data sets.

Analysis: For continuous endpoints, fit its treatment response model (MMRM) for each completed data set. For the primary and secondary key efficacy endpoints [IGA (0,1), EASI75,

EASI90, SCORAD75, and 4-point improvement from baseline in Itch NRS], the binary outcomes will be derived from the imputed data for each patient before fitting the logistic regression model.

The number of imputed data sets will be $m=100$ and a 6-digit seed value will be pre-specified for each analysis. Within the program, the seed will be used to generate the m seeds needed for imputation. The initial seed values are given in [Table JAHM.6.2](#).

Table JAHM.6.2. Seed Values for Multiple Imputation

Analysis	Seed value
Proportion of patients achieving IGA of 0 or 1 with a ≥ 2 -point improvement from baseline at Week 16 using the primary censoring rule	223450
Percent change from baseline in EASI score at 16 weeks using the primary censoring rule. EASI75 and EASI90 will leverage imputation from EASI and therefore do not need a new seed number.	223451
Proportion of patients achieving SCORAD75 at 16 week using the primary censoring rule, with data up to rescue	223452
Proportions of patients achieving a 4-point improvement from baseline in Itch NRS at Week 16 using the primary censoring rule	223453
Mean change from baseline in Skin Pain NRS at Week 16 using the primary censoring rule	223454
Mean change from baseline in the score of Item 2 of the ADSS at Week 16 using the primary censoring rule	223455

Abbreviations: ADSS = Atopic Dermatitis Sleep Scale; EASI = Eczema Area and Severity Index score; IGA = Investigator's Global Assessment for AD; NRS = Numeric Rating Scale; SCORAD = SCORing Atopic Dermatitis.

The final inference on treatment difference is conducted from the multiple datasets using Rubin's combining rules, as implemented in SAS® PROC MIANALYZE.

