6.4.5. Tipping Point Analyses

To investigate the missing data mechanism, sensitivity analyses using multiple imputation (MI) under the missing not at random assumption will be provided for the following primary and key secondary objectives:

- IGA (0,1) with ≥ 2 -point improvement at Week 16, baricitinib 1-mg, 2-mg and 4-mg compared to placebo
- EASI percent change from baseline to Week 16, baricitinib 1-mg, 2-mg and 4-mg compared to placebo
- Itch NRS 4-point improvement from baseline to Week 16, baricitinib 1-mg, 2-mg and 4-mg compared to placebo

All patients in the ITT population will be included. Data after the occurrence of intercurrent events (after application of the primary censoring rule) will be set to missing.

Within each analysis, a most extreme case will be considered, in which all missing data for patients randomized to baricitinib 1-mg, 2-mg or 4-mg will be imputed using the worst possible result and all missing data for patients randomized to placebo will be imputed with the best possible result. Treatment differences will be analyzed using logistic regression or ANCOVA (Section 6.1) as appropriate.

For continuous variables, the following process will be used to determine the tipping point:

1. To handle intermittent missing visit data, a Markov chain Monte Carlo method (SAS® Proc MI with MCMC option) will be used to create a monotone missing pattern.
2. A set of Bayesian regressions (using SAS® Proc MI with MONOTONE option) will be used for the imputation of monotone dropouts. Starting from the first visit with at least 1 missing value, the regression models will be fit sequentially with treatment as a fixed effect and values from the previous visits as covariates.
3. A delta score is added to all imputed scores at the primary time point for patients in the baricitinib treatment groups, thus worsening the imputed value. The delta score is capped for patients based on the range of the outcome measure being analyzed.
4. Treatment differences between baricitinib and placebo are analyzed for each imputed dataset using ANCOVA (Section 6.1). Results across the imputed datasets are aggregated using SAS® Proc MIANALYZE in order to compute a p-value for the treatment comparisons for the given delta value.

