6.11. Efficacy Analyses

The general methods used to summarize efficacy data, including the definition of baseline value for assessments are described in Section 6.2. The censoring rules applied to data as well as imputation methods are described in Section 6.4.

[Table JAHM.6.4](#) includes the descriptions and derivations of the primary, secondary, and exploratory efficacy outcomes.

Table JAHM.6.5 provides the detailed analyses including analysis type, method and imputation, population, time point, and comparisons for efficacy analyses.

Table JAHM.6.4. Description and Derivation of Primary, Secondary and Exploratory Efficacy Outcomes

Measure	Description	Variable	Derivation / Comment	Imputation Approach if Missing Components
Validated Investigator's Global Assessment for AD (IGA)	The validated Investigator's global assessment of the patient's overall severity of their AD, based on a static, numeric 5-point scale from 0 (clear) to 4 (severe). The score is based on an overall assessment of the degree of erythema, papulation/induration, oozing/crusting, and lichenification.	▪ IGA score	Single item. Range: 0 to 4 0 represents "clear" 4 represents "severe"	Single item, missing if missing.
		▪ Change from baseline in IGA score	Change from baseline: observed IGA score – baseline IGA score	Missing if baseline or observed value is missing.
		▪ IGA [0,1] with ≥2-point improvement ▪ IGA [0]	
 ▪ Observed score of 0 or 1 and change from baseline ≤-2 ▪ Observed score of 0 	
 ▪ Missing if baseline or observed value is missing. ▪ Single item, missing if missing.

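### Section 6.4.4 derives responders from regression-imputed scores with no ordinal model, range or rounding rule, so pMI response rates for IGA(0,1) and EASI90 can be well off among imputed patients

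*SAP*

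**What the plan says.** Section 6.4.4 uses pMI as a sensitivity analysis for the primary endpoint and the Week 16 key secondary endpoints. Step 3 gives one engine for all of them: "Run Bayesian regression in SAS® PROC MI on this data to impute missing values for visit" t, using baseline covariates and earlier visits, with placebo data alone informing the model. Scores are imputed first and dichotomised second: "The binary outcomes will then be derived from the imputed data". For IGA(0,1), EASI75, EASI90, SCORAD75 and 4-point Itch, "the binary outcomes will be derived from the imputed data for each patient before fitting the logistic regression model".

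Three other places bear on this:

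- Table JAHM.6.4 describes IGA as a 5-point scale from 0 to 4 and defines response as "Observed score of 0 or 1 and change from baseline ≤-2". It gives EASI a range of 0 to 72 and defines EASI90 as a percent change of -90 or lower, with no floor at -100.
- Table JAHM.6.2 assigns a seed to percent change in EASI and adds that "EASI75 and EASI90 will leverage imputation from EASI and therefore do not need a new seed number". It is therefore unclear whether the imputed variable is the score or its percent change.
- In the tipping-point analysis (Section 6.4.5), "The delta score is capped for patients based on the range of the outcome measure being analyzed". Section 6.4.4 has no corresponding sentence about scale range.

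**The concern.** The IGA definition presupposes whole numbers. A continuous regression draw is almost never exactly 0 or 1, and a value such as 1.3 has no assigned category. For a patient with baseline IGA 3, an unrounded 1.3 also fails the 2-point criterion, since 1.3 - 3 = -1.7. EASI cannot be negative, but a regression draw can be, and a negative value is a change below -100%, which meets the EASI90 definition.

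The plan fixes seeds to six digits but leaves open the step that decides who is a responder. Two programmers could follow Section 6.4.4 and report different results. If few imputed IGA responders survive the cut, pMI moves toward nonresponder imputation (NRI), the method it is meant to test. For EASI75, EASI90 and SCORAD75 the tipping-point list in Section 6.4.5 offers no alternative, although Table JAHM.6.1 names all three for tipping point. EASI75 is also co-primary for Japan (Section 6.6).

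**Working it through.** **1. The plan's own figure.** Section 6.4.4 states no number. The reproducible figure is the power in Section 6.1: above 90% with 240 placebo and 120 per baricitinib arm, response 10% against 25% and 30%, two-sided 0.05.

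Power = Φ[(Δ - 1.96·SE0)/SE1], with SE0 pooled and SE1 unpooled.

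- 2-mg: (0.15 - 1.96 × 0.0399)/0.0440 = 1.63, giving 94.9%.
- 4-mg: (0.20 - 1.96 × 0.0417)/0.0461 = 2.57, giving 99.5%.

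The claim reproduces, and pMI plays no part in it.

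**2. IGA, normal approximation.** The 10% response is the SAP's placebo assumption. The category split 2/8/20/40/30% for scores 0 to 4 is mine.

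- Mean = 0.08 + 0.40 + 1.20 + 1.20 = 2.88.
- Variance = (0.08 + 0.80 + 3.60 + 4.80) - 2.88² = 0.986, so SD = 0.99.
- Exactly 0 or 1: probability 0.
- Unrounded cut at 1: Φ[(1 - 2.88)/0.99] = 2.9%.
- Rounded (below 1.5): Φ[(1.5 - 2.88)/0.99] = 8.2%.

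Across four assumed splits with 10% responders, the unrounded cut gives 2.7% to 3.8% and rounding gives 7.6% to 10.6%.

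**3. IGA, sequential simulation.** Six visits, visit correlation 0.6 to 0.8 and 26% to 44% censored (all assumed), with Bayesian normal regression fitted to observed placebo data.

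| Censoring | True rate | Unrounded cut at 1 | Rounded |
|---|---|---|---|
| Unrelated to severity | about 10% | 2.9% to 3.4% | 8.2% to 8.7% |
| Related to severity | 5.4% to 7.5% | 1.5% to 2.4% | 4.6% to 6.8% |

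If 96 of 240 placebo patients were imputed, 9.6 expected responders would become about 2.9 under the unrounded cut.

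**4. EASI90 among imputed patients (assumed shapes).**

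| Assumed EASI shape | True EASI90 | Normal-regression draws |
|---|---|---|
| Right-skewed, few near-clear (sequential simulation) | 0.2% to 3.8% | 4.4% to 14.5% (3% to 12% of draws below -100%) |
| Right-skewed, gamma ratio to baseline with mean 0.7 | 4.3% | 11.3% (7.5% of draws below zero) |
| Near-clear cluster, drawn as percent change | 3.1% to 9.2% | 4.2% to 8.6% |
| Near-clear cluster, drawn as score | 3.1% to 9.2% | 6.2% to 10.7% |

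With the cluster, the ratio to truth runs from about 0.75 to 2.0 and depends on the imputation scale. EASI75 is less affected. In the sequential runs its ratio to truth lay between about 0.9 (15.0% becoming 13.4%) and 1.9 (8.5% becoming 15.9%); in a further simulation it barely moved.

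**5. Does predictive mean matching help?** In that further simulation under assumed shapes:

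| Quantity | True | Normal draws | Matched |
|---|---|---|---|
| IGA(0,1) | 10% | 3.6% unrounded, 9.1% rounded | 9.7% |
| EASI90 | 4.5% | 11.9% | 4.7% |
| EASI90, severity-related censoring | 2.3% | 7.5% | 2.7% |

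**6. Rough effect on the treatment difference.** Assume 50% of placebo and 30% of baricitinib patients are imputed, with the same error in both arms.

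- EASI90: error 11.3 - 4.3 = 7.0 points. The shift is 3.5 points on placebo and 2.1 on baricitinib, net 1.4 against baricitinib.
- IGA, unrounded: error 10 - 3 = 7 points, net 1.4 in favour of baricitinib.
- IGA, rounded: error 10 - 8 = 2 points, net 1.0 - 0.6 = 0.4.

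The planned IGA differences are 15 and 20 points. No figures were run for SCORAD75 or 4-point Itch.

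**The case against.** The strongest reply is that Section 6.4.4 is incomplete rather than wrong. It never says that the regression is linear or the draws unbounded; a reader might infer both, but they are the default reading of its wording and not a statement in it. This stands, and the point is put accordingly. A different intended model would still have to be named.

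A reader might also infer that imputed IGA responders all but disappear. That needs an unrounded cut, or a literal test for equality with 0 or 1. Any workable program must map a draw to a category, and rounding restores most of the rate. This stands too, except that the plan does not say to round.

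Nor do the documents support a firm statement that EASI90 is inflated, or that the odds ratio is pulled toward 1. The SAP gives no EASI distribution and no rescue rate, and a near-clear cluster can remove or reverse the inflation.

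The contrast with Section 6.4.5 is limited: that section caps the delta, not imputed values in general. Finally, pMI is one of several sensitivity analyses in Section 6.11.3. For IGA and Itch the tipping-point analysis imputes the binary response directly, so it avoids this problem. These replies limit the consequence; they do not supply the missing rule.

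**Conclusion.** The concern holds as a defect in one sensitivity analysis. Section 6.4.4 dichotomises imputed scores without saying how those scores are kept to possible values. Under continuous normal-regression draws, a true 10% IGA response among imputed patients is counted as about 3% to 4% with an unrounded cut, or about 8% to 11% with rounding. Imputed EASI90 can be two- to threefold too high or more when EASI is right-skewed with few near-clear patients, but this is a risk that depends on the distribution. EASI75 is less exposed.

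The sizes rest on assumed IGA splits, EASI shapes, visit correlations and censored shares, and describe imputed patients only. The net effect on the treatment difference is probably small, because the error occurs in every arm; the rough figure of 1.4 points depends on the assumed imputed shares. No changed conclusion has been shown. The primary NRI test and the sample size are unaffected.

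**What to change.** In step 3 of Section 6.4.4, still fitting on placebo only:

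- impute IGA by an ordinal logistic model (MONOTONE LOGISTIC) or predictive mean matching (MONOTONE REGPMM), or at least state rounding to the nearest category before dichotomising;
- impute EASI, SCORAD and the weekly diary scores by predictive mean matching (MONOTONE REGPMM);
- state whether EASI is imputed as a score or as percent change.

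Clipping EASI at 0 is not enough, because a clipped value is a 100% improvement and still counts as EASI90.

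The cost is a procedure option and a sentence or two in the SAP. The downside is small: matching donors are limited to placebo patients still uncensored at that visit, a selected group. In the simulation with severity-related censoring the matched EASI90 rate nevertheless stayed close to the truth (2.7% against 2.3%).

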6.4.5. Tipping Point Analyses

To investigate the missing data mechanism, sensitivity analyses using multiple imputation (MI) under the missing not at random assumption will be provided for the following primary and key secondary objectives:

- IGA (0,1) with ≥ 2 -point improvement at Week 16, baricitinib 1-mg, 2-mg and 4-mg compared to placebo
- EASI percent change from baseline to Week 16, baricitinib 1-mg, 2-mg and 4-mg compared to placebo
- Itch NRS 4-point improvement from baseline to Week 16, baricitinib 1-mg, 2-mg and 4-mg compared to placebo

All patients in the ITT population will be included. Data after the occurrence of intercurrent events (after application of the primary censoring rule) will be set to missing.

Within each analysis, a most extreme case will be considered, in which all missing data for patients randomized to baricitinib 1-mg, 2-mg or 4-mg will be imputed using the worst possible result and all missing data for patients randomized to placebo will be imputed with the best possible result. Treatment differences will be analyzed using logistic regression or ANCOVA (Section 6.1) as appropriate.

For continuous variables, the following process will be used to determine the tipping point:

1. To handle intermittent missing visit data, a Markov chain Monte Carlo method (SAS® Proc MI with MCMC option) will be used to create a monotone missing pattern.
2. A set of Bayesian regressions (using SAS® Proc MI with MONOTONE option) will be used for the imputation of monotone dropouts. Starting from the first visit with at least 1 missing value, the regression models will be fit sequentially with treatment as a fixed effect and values from the previous visits as covariates.
3. A delta score is added to all imputed scores at the primary time point for patients in the baricitinib treatment groups, thus worsening the imputed value. The delta score is capped for patients based on the range of the outcome measure being analyzed.
4. Treatment differences between baricitinib and placebo are analyzed for each imputed dataset using ANCOVA (Section 6.1). Results across the imputed datasets are aggregated using SAS® Proc MIANALYZE in order to compute a p-value for the treatment comparisons for the given delta value.
5. Steps 3 and 4 are repeated, and the delta value added to the imputed baricitinib scores is gradually increased. The tipping point is identified as the delta value which leads to a loss of statistical significance (aggregated p-value >0.05) when evaluating baricitinib relative to the placebo group.

As a reference, for each delta value used in Steps 3 through 5, a fixed selection of delta values (ranging from slightly negative to slightly positive) will be added to imputed values in the placebo group, and Step 4 will be performed for the combination. This will result in a 2-d table, with the columns representing the delta values added to the imputed placebo responses, and the rows representing the delta values added to the imputed baricitinib responses. Separate 2-d tables will compare each baricitinib dose group to placebo.

A similar process will be used for the categorical variables:

1. Missing responses in the baricitinib groups will be imputed with a range of low response probabilities, including probabilities of 0, 0.1, and 0.2.
2. For missing responses in the placebo group, a range of response probabilities (for example, probability = 0, 0.2 ... 1) will be used to impute the missing values. Multiple imputed datasets will be generated for each response probability.
3. Treatment differences between baricitinib and placebo are analyzed for each imputed dataset using logistic regression (Section 6.1). Results across the imputed datasets are

aggregated using SAS® Proc MIANALYZE in order to compute a p-value for the treatment comparisons for the given response probability. If the probability values do not allow for any variation between the multiple imputed datasets (for example, all missing responses in the placebo and baricitinib groups are imputed as responders and nonresponders, respectively), then the p-value from the single imputed dataset will be used.

The tipping point is identified as the response probability value within the placebo group that leads to a loss of statistical significance when evaluating baricitinib relative to placebo.

For tipping point analyses the number of imputed data sets will be $m=100$ and the seed values to start the pseudorandom number generator of SAS Proc MI (same values for MCMC option and for MONOTONE option) are given in [Table JAHM.6.3](#).

Table JAHM.6.3. Seed Values for Imputation

Analysis	Seed value
Proportion of patients achieving IGA (0,1) with ≥ 2 -point improvement at Week 16, with data up to rescue.	123470
EASI percent change from baseline to Week 16, with data up to rescue	123471
Proportions of patients achieving a 4-point improvement from baseline in Itch NRS at Week 16, with data up to rescue	123472

6.5. Multicenter Studies

This study will be conducted by multiple investigators at multiple sites internationally. The countries will be categorized into geographic regions, as described in [Section 5.2](#).

For the analysis of the primary endpoint, treatment-by-region interaction will be added to the logistic regression model as a sensitivity analysis and results from this model will be compared to the primary model (without the interaction effect). If the treatment-by-region interaction is significant at a 2-sided α level of 0.1, the nature of this interaction will be inspected as to whether it is quantitative (i.e., the treatment effect is consistent in direction across all regions but not in size of treatment effect) or qualitative (the treatment is beneficial in some but not all regions). If the treatment-by-region interaction effect is found to be quantitative, results from the primary model will be presented. If the treatment-by-region interaction effect is found to be qualitative, further inspection will be used to identify in which regions baricitinib is found to be more beneficial.

6.6. Multiple Comparisons/Multiplicity

The primary and key secondary endpoints will be adjusted for multiplicity in order to control the overall family-wise Type I error rate at a 2-sided alpha level of 0.05.

The following is a list of primary and key secondary endpoints to be tested. The subscript for **H** denotes dose (4-mg, 2-mg, 1-mg), the numerical identifier of the endpoint within the dose, and the type of hypothesis (0 for null, 1 for alternative), respectively.

Primary Null Hypotheses:

- **H_{4,1,0}**: Proportion of baricitinib 4-mg patients achieving IGA of 0 or 1 with a ≥ 2 -point improvement from baseline at Week 16 is less than or equal to the proportion of placebo patients achieving IGA of 0 or 1 with a ≥ 2 -point improvement from baseline at Week 16
- **H_{2,1,0}**: Proportion of baricitinib 2-mg patients achieving IGA of 0 or 1 with a ≥ 2 -point improvement from baseline at Week 16 is less than or equal to the proportion of placebo patients achieving IGA of 0 or 1 with a ≥ 2 -point improvement from baseline at Week 16

Key Secondary Null Hypotheses:

- **H_{4,2,0}**: Proportion of baricitinib 4-mg patients achieving EASI75 is less than or equal to the proportion of placebo patients achieving EASI75 at Week 16 [EASI75]
- **H_{4,3,0}**: Proportion of baricitinib 4-mg patients achieving a 4-point improvement in Itch NRS is less than or equal to the proportion of placebo patients achieving a 4-point improvement in Itch NRS at Week 16 [ITCH W16]
- **H_{4,4,0}**: Percent change from baseline in EASI score for baricitinib 4-mg patients is greater than or equal to the percent change from baseline in EASI score for placebo patients at Week 16 [EASI PCFB]
- **H_{4,5,0}**: Proportion of baricitinib 4-mg patients achieving a 4-point improvement in Itch NRS is less than or equal to the proportion of placebo patients achieving a 4-point improvement in Itch NRS at Week 4 [ITCH W4]
- **H_{4,6,0}**: Proportion of baricitinib 4-mg patients achieving SCORAD75 is less than or equal to the proportion of placebo patients achieving SCORAD75 at Week 16 [SCORAD75]
- **H_{4,7,0}**: Proportion of baricitinib 4-mg patients achieving EASI90 is less than or equal to the proportion of placebo patients achieving EASI90 at Week 16 [EASI 90]
- **H_{4,8,0}**: Mean change from baseline in Skin Pain NRS for baricitinib 4-mg patients is greater than or equal to the mean change from baseline in Skin Pain NRS for placebo patients at Week 16 [PAIN W16]
- **H_{4,9,0}**: Mean change from baseline in the score of Item 2 of the ADSS for baricitinib 4-mg patients is greater than or equal to the mean change from baseline in the score of Item 2 of the ADSS for placebo patients at Week 16 [ADSS2 W16]
- **H_{4,10,0}**: Proportion of baricitinib 4-mg patients achieving a 4-point improvement in Itch NRS is less than or equal to the proportion of placebo patients achieving a 4-point improvement in Itch NRS at Week 2 [ITCH W2]
- **H_{4,11,0}**: Mean change from baseline in the score of Item 2 of the ADSS for baricitinib 4-mg patients is greater than or equal to the mean change from baseline in the score of Item 2 of the ADSS for placebo patients at Week 1 [ADSS2 W1]
- **H_{4,12,0}**: Proportion of baricitinib 4-mg patients achieving a 4-point improvement in Itch NRS is less than or equal to the proportion of placebo patients achieving a 4-point improvement in Itch NRS at Week 1 [ITCH W1]
- **H_{2,2,0}**: Proportion of baricitinib 2-mg patients achieving EASI75 is less than or equal to the proportion of placebo patients achieving EASI75 at Week 16 [EASI75]
- **H_{2,3,0}**: Proportion of baricitinib 2-mg patients achieving a 4-point improvement in Itch NRS is less than or equal to the proportion of placebo patients achieving a 4-point improvement in Itch NRS at Week 16 [ITCH W16]

- **H_{2,4,0}**: Percent change from baseline in EASI score for baricitinib 2-mg patients is greater than or equal to the percent change from baseline in EASI score for placebo patients at Week 16 [EASI PCFB]
- **H_{2,5,0}**: Proportion of baricitinib 2-mg patients achieving a 4-point improvement in Itch NRS is less than or equal to the proportion of placebo patients achieving a 4-point improvement in Itch NRS at Week 4 [ITCH W4]
- **H_{2,6,0}**: Proportion of baricitinib 2-mg patients achieving SCORAD75 is less than or equal to the proportion of placebo patients achieving SCORAD75 at Week 16 [SCORAD75]
- **H_{2,7,0}**: Proportion of baricitinib 2-mg patients achieving EASI90 is less than or equal to the proportion of placebo patients achieving EASI90 at Week 16 [EASI90]
- **H_{2,8,0}**: Mean change from baseline in Skin Pain NRS for baricitinib 2-mg patients is greater than or equal to the mean change from baseline in Skin Pain NRS for placebo patients at Week 16 [PAIN W16]
- **H_{2,9,0}**: Mean change from baseline in the score of Item 2 of the ADSS for baricitinib 2-mg patients is greater than or equal to the mean change from baseline in the score of Item 2 of the ADSS for placebo patients at Week 16 [ADSS2 W16]
- **H_{2,10,0}**: Proportion of baricitinib 2-mg patients achieving a 4-point improvement in Itch NRS is less than or equal to the proportion of placebo patients achieving a 4-point improvement in Itch NRS at Week 2 [ITCH W2]
- **H_{2,11,0}**: Mean change from baseline in the score of Item 2 of the ADSS for baricitinib 2-mg patients is greater than or equal to the mean change from baseline in the score of Item 2 of the ADSS for placebo patients at Week 1 [ADSS2 W1]
- **H_{2,12,0}**: Proportion of baricitinib 2-mg patients achieving a 4-point improvement in Itch NRS is less than or equal to the proportion of placebo patients achieving a 4-point improvement in Itch NRS at Week 1 [ITCH W1]
- **H_{1,1,0}**: Proportion of baricitinib 1-mg patients achieving IGA of 0 or 1 with a ≥ 2 -point improvement from baseline at Week 16 is less than or equal to the proportion of placebo patients achieving IGA of 0 or 1 with a ≥ 2 -point improvement from baseline at Week 16 [IGA0-1]
- **H_{1,2,0}**: Proportion of baricitinib 1-mg patients achieving EASI75 is less than or equal to the proportion of placebo patients achieving EASI75 at Week 16 [EASI75]
- **H_{1,3,0}**: Proportion of baricitinib 1-mg patients achieving a 4-point improvement in Itch NRS is less than or equal to the proportion of placebo patients achieving a 4-point improvement in Itch NRS at Week 16 [ITCH W16]
- **H_{1,4,0}**: Percent change from baseline in EASI score for baricitinib 1-mg patients is greater than or equal to the percent change from baseline in EASI score for placebo patients at Week 16 [EASI PCFB]
- **H_{1,5,0}**: Proportion of baricitinib 1-mg patients achieving a 4-point improvement in Itch NRS is less than or equal to the proportion of placebo patients achieving a 4-point improvement in Itch NRS at Week 4 [ITCH W4]
- **H_{1,6,0}**: Proportion of baricitinib 1-mg patients achieving SCORAD75 is less than or equal to the proportion of placebo patients achieving SCORAD75 at Week 16 [SCORAD75]
- **H_{1,7,0}**: Proportion of baricitinib 1-mg patients achieving EASI90 is less than or equal to the proportion of placebo patients achieving EASI90 at Week 16 [EASI90]

- **H_{1,8,0}**: Mean change from baseline in Skin Pain NRS for baricitinib 1-mg patients is greater than or equal to the mean change from baseline in Skin Pain NRS for placebo patients at Week 16 [PAIN W16]
- **H_{1,9,0}**: Mean change from baseline in the score of Item 2 of the ADSS for baricitinib 1-mg patients is greater than or equal to the mean change from baseline in the score of Item 2 of the ADSS for placebo patients at Week 16 [ADSS2 W16]
- **H_{1,10,0}**: Proportion of baricitinib 1-mg patients achieving a 4-point improvement in Itch NRS is less than or equal to the proportion of placebo patients achieving a 4-point improvement in Itch NRS at Week 2 [ITCH W2]
- **H_{1,11,0}**: Mean change from baseline in the score of Item 2 of the ADSS for baricitinib 1-mg patients is greater than or equal to the mean change from baseline in the score of Item 2 of the ADSS for placebo patients at Week 1 [ADSS2 W1]
- **H_{1,12,0}**: Proportion of baricitinib 1-mg patients achieving a 4-point improvement in Itch NRS is less than or equal to the proportion of placebo patients achieving a 4-point improvement in Itch NRS at Week 1 [ITCH W1]

The multiple testing procedure is specified by [Figure JAHM.6.1](#).

[figure not shown]

Figure JAHM.6.1. Illustration of graphical multiple testing procedure with initial α allocation and weights.

The primary null hypotheses includes testing whether each of the baricitinib 4-mg and the baricitinib 2-mg dose is less than or equal to placebo at the primary endpoint defined as the proportion of placebo patients achieving IGA of 0 or 1 and ≥ 2 point improvement from baseline at Week 16. The initial alpha allocation is split so that $H_{4,1,0}$ has 0.04 and $H_{2,1,0}$ and 0.01. Together with these primary hypotheses, multiplicity adjusted analyses will be performed on key secondary null hypotheses to control the overall family wise Type I error rate at a 2-sided alpha level of 0.05. The graphical multiple testing procedure described in Bretz et al. (2011), which is a closed testing procedure will be used; hence it strongly controls the family-wise error rate across all endpoints (Alosh et al. 2014).

If $H_{4,1,0}$ and $H_{2,1,0}$ are not rejected, no further testing is conducted as the α for that test is considered “spent” and cannot be passed to other endpoints. If $H_{4,1,0}$ or $H_{2,1,0}$ is rejected, the testing process continues in either branches (starting with $H_{4,1,0}$ and $H_{2,2,0}$ respectively), with α propagated according to the weights on the corresponding edges displayed in [Figure JAHM.6.1](#), as long as each hypothesis in the sequence can be rejected at its allocated α level. Each time a hypothesis is rejected, the graph is updated to reflect the reallocation of α , which is considered “recycled” by Alosch et al. (2014). This iterative process of updating the graph and reallocating α is repeated until all hypotheses have been tested or when no remaining hypotheses can be rejected at their corresponding α levels.

For Japan, the same testing strategy described in the [Figure JAHM.6.1](#) will be used, however, the proportion of patients achieving EASI75 and IGA of 0 or 1 at Week 16 are considered co-primary. Both endpoints have to meet statistical significance compared with placebo with a specific α level based on the graphical multiple testing procedure in order to demonstrate a superiority of a given baricitinib dose (baricitinib 4-mg and/or baricitinib 2-mg) compared with placebo. That is, $H_{4,1,0}$ and $H_{4,2,0}$ have to be rejected in order to demonstrate the superiority of baricitinib 4-mg compared with placebo and $H_{2,1,0}$ and $H_{2,2,0}$ have to be rejected in order to demonstrate the superiority of baricitinib 2-mg compared with placebo.

There will be no adjustment for multiple comparisons for any other analyses.

